For patients with primary CNS tumors with measurable disease at baseline who have a baseline tumor assessment per the investigator according to Response Assessment in Neuro-Oncology (RANO) criteria and receive at least one dose of alectinib:

- ORR, DOR, and PFS in all ALK fusion-positive patients who have measurable disease at baseline as determined by both the investigator and BICR
- OS

For patients with solid tumors without ALK fusions, harboring defined ALK mutations (R1275Q, F1245C, F1174X, with X being any other amino acid) and receive at least one dose of alectinib:

- ORR, DOR, and PFS as determined by the investigator and by BICR according to RECIST v1.1
- CNS ORR and DOR in patients with CNS metastases at baseline by BICR according to RECIST v1.1
- OS

For patients with CUP who receive at least one dose of alectinib:

- ORR, DOR, and PFS as determined by both the investigator and BICR according to RECIST v1.1
- CNS ORR and DOR in patients with CNS metastases at baseline, as determined by BICR according to RECIST v1.1
- OS

Exploratory Efficacy Objective

The exploratory efficacy objective for this study is to evaluate the efficacy of alectinib in patients with ALK-positive CUP and non-CUP solid tumors who receive at least one dose of alectinib on the basis of the following endpoints:

- ORR, DOR, and PFS, as determined by the investigator and by BICR according to RECIST v1.1
- CNS ORR and DOR in patients with CNS metastases at baseline by BICR according to RECIST v1.1
- OS

Safety Objectives

The safety objective for this study is to evaluate the safety of alectinib in all dosed patients on the basis of the following endpoints:

- Incidence and severity of adverse events, including serious adverse events, with severity determined according to National Cancer Institute Common Terminology Criteria for Adverse Events Version 5.0 (NCI CTCAE v5.0)
- Change from baseline in targeted vital signs
- Change from baseline in targeted clinical laboratory test results

Pharmacokinetic Objective

The pharmacokinetic (PK) objective for this study is to characterize the alectinib PK profile on the basis of the following endpoint:

• Plasma concentrations of alectinib and its metabolite(s) as applicable at specified timepoints

Exploratory Biomarker Objectives

The exploratory biomarker objectives for this study are as follows:

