3.3.3 Rationale for Patient Population and Analysis Groups

The study population consists of patients with ALK-positive locally advanced or metastatic solid tumors other than lung cancer who have either exhausted or are unsuitable to receive the standard of care for their diagnosed malignancy. See Section 1.1 for details on ALK fusions and ALK alterations and Section 1.4 for more information about the study population.

The primary analysis will be performed on ALK fusion solid tumors (excluding patients with CUP and CNS primary tumors) that are measurable at baseline, as assessed by the investigator according to Response Evaluation Criteria in Solid Tumors Version 1.1 (RECIST), which is expected to be the main population recruited in the study.

Patients with CUP are also allowed in the study, and data will be analyzed separately from the data in the primary analysis. This will be done to preserve the primary analysis population of patients with ALK fusion solid tumors. Analyzing patients with CUP as a part of the primary analysis population would lead to increased risk of enrolling patients with misdiagnosed ALK-positive lung cancer.

Patients with primary CNS tumors are allowed in the study, and data will be analyzed separately as their disease is assessed using a different set of criteria (i.e., the RANO criteria).

Patients with tumors harboring selected ALK-activating mutations are also allowed in the study. However, data will be analyzed separately from data in the primary analysis because evidence of benefit with ALK inhibitors in these tumors is less robust than for ALK fusion–driven malignancies and is primarily limited to neuroblastoma.

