Response will be assessed by the investigator on the basis of the CT and MRI scans according to RECIST v1.1 (see Appendix 5) or, for patients with primary CNS tumors, RANO criteria, which include neurological examination and corticosteroid use (see Appendix 6).

In addition, scans will be sent for BICR for assessment of responses according to RECIST v1.1 and, for patients with primary CNS tumors, according to RANO criteria.

Assessments performed by BICR will not be shared with the investigator and will have no impact on the management of the patient.

Tumor assessments performed as standard-of-care prior to obtaining informed consent and within 28 days prior to the first dose may be considered as baseline assessment if they satisfy the protocol criteria.

Scheduled tumor assessments should be kept according to the original scheduled based on the date of first dose administration, regardless of clinical visits delays and drug interruptions. At the investigator's discretion, tumor assessment may be repeated at any time if progressive disease is suspected (for example, in case of symptomatic deterioration).

An objective response should be confirmed by repeat assessments at least 4 weeks after initial documentation. No additional assessment is planned for 4 weeks after the initial response, but every effort should be made to obtain confirmation of response, even if a patient who has initially responded is withdrawn from study treatment for any reasons other than progression or death.

Patients who discontinue study treatment for any reason other than progression of disease or death should continue to have regular disease assessments every 8 weeks per the schedule of assessments (see Appendix 1) until progression.

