6. STATISTICAL CONSIDERATIONS AND ANALYSIS PLAN

The following populations are defined:

- The response-evaluable population is defined as all patients with ALK fusion (excluding patients with CUP and CNS primary tumors) solid tumors with measurable disease at baseline evaluable according to RECIST v1.1 who receive at least one dose of study drug.
- All populations are defined according to the investigator or by blinded independent center review (BICR), depending on who is assessing the endpoint.
- The response-evaluable population with measurable CNS disease at baseline is defined as all patients with measurable CNS disease at baseline evaluable according to RECIST v1.1 who receive at least one dose of study drug.
- The primary CNS tumor response-evaluable population is defined as all patients with ALK fusion CNS primary tumors with measurable disease at baseline evaluable according to RANO criteria who receive at least one dose of study treatment.
- The CUP response-evaluable population is defined as all patients with CUP with measurable disease at baseline evaluable according to RECIST v1.1 who receive at least one dose of study drug.
- The ALK-mutations response-evaluable population is defined as all patients with ALK mutations with measurable disease at baseline evaluable according to RECIST v1.1 who receive at least one dose of study drug.

The primary analysis will be performed on the response-evaluable population.

Secondary analyses will be performed on the response evaluable population, the measurable CNS disease at baseline response-evaluable population, the primary CNS tumor response evaluable population, the CUP response-evaluable population, and the ALK mutation response-evaluable population, separately. The DOR will be assessed in the patients with confirmed or unconfirmed objective response, as appropriate.

Alectinib—F. Hoffmann-La Roche Ltd

Safety analyses will be performed on all enrolled patients who receive at least one dose of study drug.

Details of all above analyses will be provided in the Statistical Analysis Plan.

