6.4.2.1 Secondary Endpoint Definitions

The secondary endpoint definitions are as follows.

Confirmed Objective Response Rate

Proportion of patients with a confirmed objective response by BICR. An objective response is defined as a CR or a PR per RECIST v1.1. Confirmation of objective response is required (confirmed \geq 28 days apart in two separate tumor assessments).

Patients not meeting this criterion (including patients without a post-baseline tumor assessment) will be considered non-responders.

An analysis of this endpoint will also be performed on the basis of RANO criteria assessed by investigator and BICR in patients with primary CNS tumors. Confirmation of objective response is not required for patients with ALK mutations.

Duration of Response

Duration of response is defined as the time from the date of the first occurrence of a CR or a PR (whichever status is recorded first) to the date of the first documented disease progression or death due to any causes, whichever occurred first. The DOR will be assessed in patients who had a confirmed objective response during the study, as determined by the investigator or BICR per RECIST v1.1. Patients who have not progressed or died at the time of analysis will be censored at the last tumor assessment date. If no tumor assessments are performed after the date of the first occurrence of a CR or a PR, DOR will be censored at the date of the first occurrence of a CR or a PR. The Kaplan-Meier method will be used to estimate the median DOR with 95% CIs.

An analysis of this endpoint will also be performed on the basis of RANO criteria assessed by the investigator and BICR in patients with primary CNS tumors. Confirmation of objective response is not required for patients with ALK mutations.

Progression-Free Survival

Progression-free survival is defined as the time from the first date of treatment to the date of first documented disease progression or death, whichever occurs first. Disease progression will be assessed by the investigator or the BICR using RECIST v1.1. Patients who have not experienced disease progression or died at the time of analysis will be censored at the last tumor assessment date. Patients with no post-baseline tumor assessment will be censored at the first date of treatment. The Kaplan-Meier method will be used to estimate the median PFS with 95% CIs.

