## 5.3 PRIMARY ENDPOINT ANALYSIS

## 5.3.1 Definition of Primary Endpoint

The primary efficacy endpoint is confirmed ORR as determined by the investigator in patients with ALK fusion solid tumors (excluding enrolled patients with CUP and CNS primary tumors). An objective response is defined as a CR or a PR according to RECIST v1.1. Confirmation of objective response is required (confirmed ≥ 28 days apart in two separate tumor assessments). Patients not meeting this criterion (including patients without a post-baseline tumor assessment) will be considered as non-responders. ORR is defined as the proportion of patients with measurable disease at baseline who have an objective response in the response-evaluable population.

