#### 5.4.2.7 Efficacy in Patients with Solid Tumors without ALK Fusions, Harboring Defined ALK Mutations (R1275Q, F1245C, F1174X, with X being any other amino acid)

For patients with solid tumors without ALK fusions, harboring defined ALK mutations (R1275Q, F1245C, F1174X, with X being any other amino acid) and receive at least one dose of alectinib:

- ORR, DOR, and PFS as determined by the investigator and by BICR according to RECIST v1.1
- CNS ORR and DOR in patients with CNS metastases at baseline by BICR according to RECIST v1.1
- OS

Confirmation of objective response is not required.

The analysis methods are the same as for the respective endpoints defined above.

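### Overall ORR and DOR in the ALK-mutation cohort rest on unconfirmed responses, without a stated reason, and are not like-for-like with the confirmed figures of the other cohorts

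*Protocol*

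**What the plan says.** The Synopsis and Protocol 2.1.2 give the ALK-mutation cohort a plain list: "ORR, DOR, and PFS as determined by the investigator and by BICR according to RECIST v1.1", then CNS ORR and DOR, then OS. The list is silent on confirmation.

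The rule appears in Protocol 6.4.2.1. Under the ORR definition, and again under DOR, the text adds: "Confirmation of objective response is not required for patients with ALK mutations". SAP 5.4.2.7 repeats the waiver for the cohort as a whole: "Confirmation of objective response is not required". Neither document explains it.

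For ALK-fusion patients, SAP 5.3.1 says "Confirmation of objective response is required", in two assessments at least 28 days apart. The general DOR rule in Protocol 6.4.2.1 is "The DOR will be assessed in patients who had a confirmed objective response during the study", and SAP 5.4.2.1 agrees. The opening of Protocol Section 6 is looser: "The DOR will be assessed in the patients with confirmed or unconfirmed objective response, as appropriate". It does not say which cohort gets which rule.

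On data collection, Protocol 4.6.5 asks for repeat assessment of any objective response and says "every effort should be made to obtain confirmation of response, even if a patient who has initially responded is withdrawn from study treatment". It makes no exception for ALK mutations.

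**The concern.** The same label, ORR, covers two definitions. A reader who sees the ALK-mutation ORR in a results table next to the fusion or CUP ORR will compare them, and the mutation figure has been measured by the easier rule. A single reading past the 30% shrinkage threshold counts as a response and also starts a DOR clock.

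The choice is also hard to square with the protocol's own reasoning. Protocol 3.3.3 keeps this cohort apart because "evidence of benefit with ALK inhibitors in these tumors is less robust than for ALK" fusion-driven disease. Thinner prior evidence is not an obvious ground for a more lenient response definition. At stake is the interpretation of a secondary endpoint in a cohort that may be small, where one or two responses move the rate visibly.

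**Working it through.** **1. Confirmation rule by cohort**

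| Cohort and endpoint | Rule | Source |
|---|---|---|
| ALK fusion, overall ORR (investigator, BICR) | Confirmed, at least 28 days apart | Protocol 6.4.1, 6.4.2.1; SAP 5.3.1, 5.4.1 |
| ALK fusion, overall DOR | Confirmed responders | Protocol 6.4.2.1; SAP 5.4.2.1 |
| CUP, overall ORR and DOR | No rule of its own; takes the definitions above by reference, hence confirmed | SAP 5.4.2.8 |
| Primary CNS tumors, ORR and DOR | RANO: 4 weeks for CR and PR in high-grade glioma; in low-grade glioma stated for PR but not for CR | Protocol Appendix 6, Tables 3 and 5 |
| ALK mutation, overall ORR and DOR | Not confirmed | Protocol 6.4.2.1; SAP 5.4.2.7 |
| ALK fusion with measurable CNS metastases, CNS ORR and CNS DOR | Not confirmed | Protocol 6.4.2.1; SAP 5.4.2.4, 5.4.2.5 |

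For overall response, the ALK-mutation cohort is the only disease cohort with a waiver. For CNS response, the waiver also applies to fusion patients.

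**2. Direction for ORR**

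Every confirmed responder is also an unconfirmed responder. So in the same patients unconfirmed ORR is at least as high as confirmed ORR, with equality only if every response confirms. This needs no assumption.

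**3. Size for ORR**

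The documents give no expected rate, sample size or confirmation share for this cohort, so there is no plan figure to reproduce. Let c be the share of responding patients whose response is later confirmed. Then

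unconfirmed ORR = confirmed ORR / c.

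Take a confirmed ORR of 30% purely as a reference level (it is the SAP Section 2 threshold for the fusion cohort):

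- c = 1.00: 30 / 1.00 = 30.0%, excess 0
- c = 0.90: 30 / 0.90 = 33.3%, excess 3.3 points
- c = 0.75: 30 / 0.75 = 40.0%, excess 10.0 points

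The range for c is an assumption.

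**4. Small-cohort illustration**

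The cohort size is not fixed (Protocol 6.1). Assume 10 patients with 3 confirmed responses: 30% (Clopper-Pearson 95% CI 6.7 to 65.2). One further, unconfirmed response gives 4/10 = 40% (12.2 to 73.8). One patient shifts the point estimate by 10 points, and the intervals overlap heavily.

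**5. DOR**

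A single-scan responder who progresses at the next scheduled scan adds a duration of about 8 weeks. One with no later scan is censored at the response date and adds a patient but no follow-up. One who falls back to stable disease runs on until progression. The tendency is toward shorter durations, but unlike for ORR the direction is not certain.

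**6. Are the data there for a confirmed figure?**

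Yes. Scans are every 8 weeks (Appendix 1), continue off treatment until progression (Protocol 4.7.1), and the primary analysis waits for 24 weeks or three assessments so that responses can be confirmed (Protocol 6.4.1). Scans 8 weeks apart meet a 28-day rule.

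**The case against.** The best defense is that nothing is hidden. The waiver is prespecified and consistent across protocol and SAP. The cohort is analyzed separately, no test against 30% is stated for it, and no comparison between cohorts is planned. If numbers are low, SAP 5.4.2.8 allows listings or spider plots, where a single-scan response can be seen. In a small cohort, requiring confirmation also loses patients whose first response falls at their last scan. All of this stands. It limits the point to reporting and interpretation.

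Three stronger readings are tempting and should be resisted.

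- *The cohort's ORR is inflated by 10 to 16 points.* A measurement-error model can produce that, but only with an assumed per-scan SD of 7 to 10 percentage points, which implies that 26% to 51% of responses fail to confirm. With an SD of 3 to 5 the same model gives about 4 to 8 points. The documents support none of these inputs.
- *Unconfirmed response is unique to this cohort.* That is true only of overall ORR and DOR. CNS ORR and CNS DOR in fusion patients are unconfirmed too. The CUP rule is inferred by cross-reference, and the loose DOR sentence in Protocol Section 6 does not settle it.
- *The figures cannot be read beside the other cohorts at all.* They can, once a confirmed rate is derived from scans already collected and the basis is labeled.

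**Conclusion.** The point holds as a cheap improvement to a secondary, descriptive analysis. Overall ORR and DOR in the ALK-mutation cohort use a more lenient response definition than the general one, no reason is given, and the Synopsis does not show the difference. That the unconfirmed ORR is at least as high as the confirmed one is certain. The amount is unknown: 3 to 10 points at a confirmed ORR of 30% if 10% to 25% of first responses fail to confirm, and nothing if all confirm. The primary analysis and its test against 30% are untouched.

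**What to change.** In SAP 5.4.2.7, limit the change to overall ORR and DOR. Report confirmed ORR (two assessments at least 28 days apart, as for the primary endpoint) and DOR in confirmed responders. Show the prespecified unconfirmed ORR and DOR separately, and label the response basis in every table. Align the two matching sentences in Protocol 6.4.2.1.

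Do not simply replace the waiver sentence in SAP 5.4.2.7. It governs the whole list there, so a blanket confirmation rule would also reach this cohort's CNS ORR and CNS DOR and put them out of step with SAP 5.4.2.4 and 5.4.2.5. State that those two endpoints stay unconfirmed, as in fusion patients.

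The cost is some wording and an extra set of table rows, with no new scans. The one real downside is that a response first seen at the last available scan does not count in the confirmed figure, though it stays visible in the unconfirmed one.

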1.1 BACKGROUND ON ALK-POSITIVE SOLID TUMORS

1.1.1 Background on ALK-Oncogene and ALK-Inhibitor Development

Anaplastic lymphoma kinase (ALK) is a cytoplasmatic membrane tyrosine kinase receptor protein encoded by the *ALK* gene. While wild-type ALK is expressed at very low levels in most normal human tissues, and its physiological expression is limited to neuronal cells (glial cells, neurons, endothelial cell, and pericytes) (Pulford et al. 1997), the *ALK* gene has been found to be rearranged, mutated, or amplified in a series of tumors (Ardini et al. 2010). In particular, chromosomal rearrangements result in ALK fusion proteins that have been shown to be constitutively active leading to increased signaling of pathways that drive uncontrolled cell growth, survival, and ultimately tumorigenesis.

Expression of these *ALK* fusion genes in mouse 3T3 fibroblasts cause cell transformation and enhanced proliferation. Inhibition of ALK activity in Ba/F3 cells transfected with the EML4-ALK fusion protein resulted in inhibition of cell growth (Ou et al. 2012). In addition, inhibition of ALK signaling demonstrated anti-tumor efficacy in two xenograft models in athymic mice, namely, the H3122 non–small cell lung cancer (NSCLC) and Karpas299 anaplastic large cell lymphoma models harboring the EML4-ALK and nucleophosmin ALK fusion proteins, respectively (Koivunen et al. 2008; Webb et al. 2009).

In NSCLC, ALK fusions are observed with a frequency of approximately 5%. In solid tumors other than NSCLC, many different ALK-fusion partners have been identified in a variety of malignancies, including, but not limited to, Spitz tumors, inflammatory myofibroplastic tumors (IMTs), thyroid cancer, digestive tract cancer, ovarian cancer, and renal cell carcinoma (Hallberg and Palmer 2013; Cao et al. 2019). However, outside of NSCLC, the frequency of ALK rearrangements in solid tumors is extremely low and estimated at about 0.2% (Ross et al. 2017). In addition to ALK fusion proteins, activating mutations in the ALK kinase domain have been found in different tumor types, including familial and sporadic cases of neuroblastoma (Lamant et al. 2000; Mossé et al. 2008; Wood et al. 2009).

Given the relatively high prevalence of ALK alterations in NSCLC, ALK inhibitor development in solid tumors has been largely limited to this indication, and to date several ALK inhibitors have been approved for advanced or metastatic ALK-positive NSCLC (Serritella and Bestvina 2020). Crizotinib (Xalkori[®]; Pfizer, Inc.) was the first ALK inhibitor approved and registered for the treatment of advanced and metastatic ALK-positive NSCLC (Sahu et al. 2013; Shaw et al. 2013). Crizotinib was granted approval for first-line treatment of patients with ALK-positive NSCLC with advanced or metastatic disease based on the results of the Phase III PROFILE 1014 study, which showed a significantly longer progression-free survival (PFS) for patients treated with

Alectinib—F. Hoffmann-La Roche Ltd 24/Protocol BO41929, Version 4

crizotinib compared with platinum-based chemotherapy (median PFS: 10.9 vs. 7.0 months) in patients with previously untreated ALK-positive NSCLC (Solomon et al. 2014). Since then, next-generation ALK inhibitors, such as alectinib, ceritinib, and brigatinib, have been granted market authorization as first- or second-line treatment for advanced and metastatic ALK-positive NSCLC (Serritella and Bestvina 2020).

Studies of patients who had progression with crizotinib treatment revealed two main reasons for treatment failure: development of resistance because of secondary mutations predominantly in *ALK* or occasionally in other genes, such as *EGFR* or *KRAS* (Katayama et al. 2011; Doebele et al. 2012; Kim et al. 2013), and CNS relapse or progression. The CNS is the primary site of initial treatment failure in approximately 46% of patients with ALK-positive NSCLC treated with crizotinib due to its poor CNS penetration (Costa et al. 2011; Chun et al. 2012; Weickhardt et al. 2012). Significant morbidity is associated with brain metastases as a direct consequence of the pathophysiology of brain metastases and as a result of the side effects of treatment required to control CNS disease, such as corticosteroids, surgery, and radiation.

